Study Protocol, Statistical Analysis Plan and Informed Consent Form

Efficacy of percutaneous laser disc decompression versus
epidural steroid and local anesthetic injection by
transforaminal approach in the treatment of lumbar radicular
pain

26.09.2022.

Study Protocol

The research is designed as a randomized controlled trial, and will be conducted at the Clinic for Anesthesiology, Reanimatology and Intensive Care Medicine of the Osijek Clinical Hospital Center after obtaining the approval of the Ethics Committee. All patients will receive a written informed consent describing the procedure to be performed, and the procedure will also be explained to them orally. After signing the informed consent, patients will be divided into 2 groups depending on whether there is diascorradicular contact or not, and then within each group depending on the method (ESI or PLDD).

Subjects will be between the ages of 18 and 65 who agree to participate in the study, which they confirm by signing the informed consent, have unilateral lumbar radicular pain that does not respond to conservative treatment, disc herniation at one level, MR verified disc herniation, pain intensity measured with the VAS scale >5 . The obtained data will be statistically processed.

Exclusion criteria will be: patients younger than 18 and older than 65 years, refusal of the patient to participate in the research, central stenosis of the lumbar canal, lumbar radicular pain caused by causes other than intervertebral disc herniation, pregnancy, allergy to steroids, local anesthetics, fentanyl, midazolam and contrast agent, positive history of prolonged bleeding, local or systemic infection, previous lumbar spine surgery, opioid abuse, proven inflammatory rheumatic disease and inflammatory bowel disease in the active phase, and other acute infections.

To observe a mean effect in the difference of numerical variables between four independent groups of subjects, with a significance level of 0.05 and a power of 0.80, the minimum required sample size is 116 subjects (29 subjects per group) (calculation made using the program G*Power version 3.1.2, Franz Faul, University of Kiel, Germany).

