Patients will have 4 measurements. The first measurement will be before the procedure, the second measurement will be at the follow-up examination after one month, the third measurement at the follow-up examination 3 months after the procedure, and the fourth measurement at the follow-up examination 6 months after the procedure. Control MR of the LS spine will be done 6 months after the procedure.

The VAS scale (Visual Analogue Scale) will be used to assess pain intensity. The questionnaires will be SF-36 (Short form health survey-36), Oswestry Disability Questionnaire Index (ODI), Pain Detect, Hospital Anxiety and Depression Scale (HADS), and the Pittsburgh Sleep Quality Index (PSQI).

From the clinical examinations, the Lasegue test, the toe-heel test and the flexion test will be performed. Among the laboratory tests, the level of interleukin 6 (IL-6), C-reactive protein (CRP), leukocyte count and differential blood count (DKS) will be determined. The mentioned parameters will be analyzed in three visits: before the procedure, one month after the procedure and after 6 months.

Statistical Analysis Plan

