Categorical data will be represented by absolute and relative frequencies. Numerical data will be described by the arithmetic mean and standard deviation in the case of distributions that follow the normal, and in other cases by the median and the limits of the interquartile range. Differences in categorical variables will be tested with the χ^2 test, and if necessary, with Fisher's exact test. The normality of the distribution of numerical variables will be tested with the Shapiro-Wilk test. Differences of normally distributed numerical variables between two independent groups will be tested with Student's t test, and in case of deviation from normal distribution with Mann-Whitney U test. Differences of normally distributed numerical variables in case of 3 or more independent groups will be tested by analysis of variance (ANOVA), or Kruskal-Wallis test (Post hoc Conover). Differences of normally distributed numerical variables between 4 measurements will be tested by analysis of variance for repeated measurements, and in case of deviation from normal distribution by Friedman test. The association of normally distributed numerical variables will be assessed by Pearson's correlation coefficient r , and in case of deviation from normal distribution by Spearman's correlation coefficient ρ (rho). All P values will be two-sided. The significance level will be set at $\alpha=0.05$. For statistical analysis, the statistical program MedCalc Statistical Software version 19.1.7 (MedCalc Software Ltd, Ostend, Belgium; <https://www.medcalc.org>; 2020) and SPSS (version 16.0, SPSS Inc., Chicago, IL, NOW).

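### The SAP's correlations are not adjusted for the four contact-by-method groups, so group differences alone can produce an association between two outcomes

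*Combined protocol and SAP*

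**What the plan says.** The Statistical Analysis Plan covers association between numerical variables in one sentence: "The association of normally distributed numerical variables will be assessed by Pearson's correlation coefficient r". The same sentence switches to Spearman's rho when the data are not normal. It does not say which variables will be paired, at which visit, in which patients, or with what adjustment. The other listed methods are tests of difference: chi-square or Fisher, t or Mann-Whitney, ANOVA or Kruskal-Wallis, and repeated-measures ANOVA or Friedman. There is no regression, ANCOVA, partial correlation or mixed model. On sidedness it says "All P values will be two-sided", and the level is 0.05.

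The Study Protocol sets out the group structure: "patients will be divided into 2 groups depending on whether there is diascorradicular contact or not, and then within each group depending on the method" (epidural injection or laser decompression). The sample-size paragraph rests on the same four groups: "the minimum required sample size is 116 subjects (29 subjects per group").

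The numerical variables include VAS and the questionnaire scores, with four measurements planned per patient. For the laboratory tests, "the level of interleukin 6 (IL-6), C-reactive protein (CRP), leukocyte count and differential blood count (DKS) will be determined" at three visits: before the procedure, at one month and at six months.

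**The concern.** The four groups drive the design and the sample size but do not appear in the association sentence. One method delivers a steroid and the other does not, so a post-procedure difference between arms in both an inflammatory marker and pain is plausible. A difference in pain is what an efficacy trial looks for. Disc-root contact is a patient characteristic and could be related to both variables at any visit.

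If one grouping factor shifts both variables, a coefficient across all patients mixes that shift with any link between the two within groups. A reader would take a significant coefficient to mean that patients with more inflammation have more pain. It might show only which procedure they had, or whether the disc touched the root. Shifts in opposite directions would do the reverse and could hide a real positive link.

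**Working it through.** **Inputs from the documents.** Four groups of 29, so N = 4 × 29 = 116, with 58 per arm and 58 per contact stratum; two-sided test at 0.05; Pearson or Spearman coefficient.

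**Assumed inputs.** The documents give no size for any group difference, so a range of shifts is used, in within-group SD units. The within-group correlation is set to zero.

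**The plan's own figure.** The protocol's calculation starts "To observe a mean effect in the difference of numerical variables between four independent groups of subjects" and gives no numerical effect size. Reading it as f = 0.25, a one-way ANOVA on four groups needs 180 patients (power 0.59 at 116). The figure of 116 is reproduced by the between-groups test of a repeated-measures ANOVA with m = 4 measurements and an assumed correlation of 0.5: λ = f²·N·m / (1 + (m − 1)ρ) = 0.0625 × 116 × 4 / 2.5 = 11.6, power 0.812 (0.796 at 112). This does not bear on the present point; 116 is used only as the number of patients correlated.

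**Correlation created by a group shift.** If a factor splitting the sample in half shifts both variables by d, it adds d²/4 to their covariance and d²/4 to each variance of 1. So r = (d²/4) / (1 + d²/4):

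- d = 0.3: 0.0225 / 1.0225 = 0.022
- d = 0.5: 0.0625 / 1.0625 = 0.059
- d = 0.8: 0.16 / 1.16 = 0.138

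With arm and contact each shifting both variables by 0.5: r = 0.125 / 1.125 = 0.111. If one of the two variables does not shift, the added covariance is zero and r = 0.

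**Rejection rate.** With 116 − 2 = 114 degrees of freedom, the test is significant when |r| exceeds 0.182. Simulation at a single visit with no within-group link (20,000 data sets; 5,000 for Spearman) gave:

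| Shift in each variable (SD) | Mean r | Raw Pearson | Raw Spearman | Pearson adjusted for four groups |
|---|---|---|---|---|
| none | 0.00 | 5.0% | 5.0% | 5.1% |
| arm 0.3 in both | 0.02 | 6.0% | 5.8% | 5.2% |
| arm 0.5 in both | 0.06 | 9.2% | 9.3% | 5.1% |
| arm 0.8 in both | 0.14 | 32.6% | 32.4% | 4.9% |
| arm 0.5 and contact 0.5 in both | 0.11 | 22.5% | 21.7% | 4.9% |
| arm 0.5 in one only | 0.00 | 4.9% | 5.1% | 5.0% |
| arm 0.8 in one only | 0.00 | 5.2% | 5.4% | 5.1% |

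The adjusted test uses 114 − 3 = 111 degrees of freedom. A separate simulation of the rank version of the adjusted test gave 4.6% to 5.5%.

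**Check with the Fisher transformation.** The standard error is 1/√113 = 0.094. At d = 0.8 the transformed r is 0.139, or 1.475 standard errors, and the test rejects about 31% of the time. At d = 0.5 it is 0.63 standard errors and about 10%. Both agree with the table.

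**Baseline.** Randomised arm has had no effect before the procedure, so it cannot systematically shift either variable. Contact can, and since it also splits the sample 58/58 the same formula applies.

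**The case against.** **No marker-pain question is stated.** This stands. The title objective is efficacy, and the protocol says only that the markers will be determined and analysed at three visits. A reader might infer that the trial sets out to test whether inflammation tracks pain; the documents do not say so. What remains is that the SAP commits to correlating numerical variables without saying which, so the weakness attaches to any pair chosen.

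**Silence is not a plan to pool.** This also stands. A reader might infer that the SAP ignores groups and visits, correlates levels rather than changes, or treats three visits per patient as 348 independent rows. It says none of these things. The coefficient could be run on change scores, at one visit, or inside one group of 29. Pooling visits would matter if done: with no group effect, the rate is 7.5%, 10.8% and 15.8% at assumed within-patient correlations of 0.3, 0.5 and 0.7. Those figures justify a sentence ruling it out; they do not describe a planned analysis. Nor is correlation strictly the only route from markers to pain, since the two-group tests could compare markers between pain categories, also unadjusted.

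**The size depends on the assumptions.** Correct. Both variables must differ between groups, and the effect is modest for one factor at 0.5 SD or less. Nothing in the documents shows that arms will differ by 0.8 SD in a marker at one or six months.

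**The raw coefficient is right for what it estimates.** If arm shifts both variables, the marginal correlation truly is non-zero, and adjustment may remove a part that runs through inflammation. This is the strongest objection, but it does not rescue the raw coefficient as evidence of a patient-level link: that link has to be assessed with arm and contact held fixed, whatever the route by which they act.

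**Conclusion.** The point holds in a limited form. As written, the SAP's sole method for associating two numerical variables makes no allowance for the design's four groups. Applied to the whole sample, it can reject well above 5% with no within-group link. For one factor at one visit the excess is negligible at 0.3 SD, small at 0.5 SD and large at 0.8 SD; two factors at 0.5 SD each give about 22%. All these shifts are assumptions, and there is no inflation if only one variable differs between groups.

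A reader might go further and infer that the trial is likely to report a false biomarker finding. The documents do not support that: they state no such analysis and give no expected differences. The randomised comparison of the two procedures is unaffected.

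**What to change.** Amend the association sentence in the Statistical Analysis Plan to say that correlations across the whole sample will be:

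- computed separately at each visit, without treating repeated visits as independent rows;
- partial correlations (Pearson, or on ranks when the data are not normal) adjusted for the four contact-by-method groups;
- reported as exploratory.

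SPSS, already named in the SAP, can do this with group indicators as the controlling variables. Change scores and a fixed list of tests are not needed to repair this point and can be left to the investigators.

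The cost is 3 degrees of freedom (114 to 111) and slightly more analysis work. No new data are needed and the sample size stays at 116.

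### No primary outcome, visit, PLDD-ESI contrast or multiplicity rule is named, so alpha = 0.05 does not control the error rate for the title question

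*Combined protocol and SAP*

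**What the plan says.** The title poses a two-treatment question: percutaneous laser disc decompression (PLDD) against transforaminal epidural injection (ESI). The Study Protocol first splits patients by disc-root contact, "and then within each group depending on the method (ESI or PLDD"), which makes four groups. The sample-size paragraph is worded "To observe a mean effect in the difference of numerical variables between four independent groups of subjects". It fixes alpha at 0.05 and power at 0.80 and arrives at 116 subjects, 29 per group. It names no variable, no visit and no numerical effect size.

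The outcomes in the Study Protocol are VAS for pain; then "The questionnaires will be SF-36 (Short form health survey-36), Oswestry Disability Questionnaire Index (ODI), Pain Detect, Hospital Anxiety and Depression Scale (HADS") plus PSQI; three clinical tests; a laboratory panel ("the level of interleukin 6 (IL-6), C-reactive protein (CRP), leukocyte count and differential blood count (DKS) will be determined"); and a control MR at 6 months. Measurements are at baseline and 1, 3 and 6 months. A later sentence reads "The mentioned parameters will be analyzed in three visits: before the procedure, one month after the procedure and after 6 months", and it is unclear whether this covers only the laboratory tests or everything listed. No outcome is labelled primary or secondary.

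The Statistical Analysis Plan gives a two-group test (t or Mann-Whitney). For three or more groups, differences "will be tested by analysis of variance (ANOVA), or Kruskal-Wallis test (Post hoc Conover"). Repeated-measures ANOVA or Friedman is given for the four measurements, and there are correlation coefficients. It closes with "All P values will be two-sided. The significance level will be set at" 0.05. No test is tied to an outcome, a visit or a treatment contrast.

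**The concern.** The nominal 0.05 protects one test chosen in advance. Here nothing is chosen in advance. The PLDD-ESI question could be answered on VAS, ODI or any other score, at 1, 3 or 6 months, pooled over contact groups or within either one, by a two-group test or after a four-group test. No success criterion says how many of these must be significant, or which.

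A claim of efficacy could therefore rest on whichever combination gave P < 0.05. A reader could not tell how many chances there had been, and a negative trial could be presented as positive without departing from the plan. The planned power has the same gap: it refers to a four-group comparison of unspecified variables, not to a test of PLDD against ESI.

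**Working it through.** **1. The plan's own figure.** Inputs from the sample-size paragraph: alpha 0.05, power 0.80, four groups, N = 116. The effect size is not given; f = 0.25 (a medium effect) is assumed.

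- One-way ANOVA, noncentrality λ = f²N, 3 and N − 4 df: f = 0.25 needs N = 180, and at N = 116 the power is 0.59. N = 116 gives 0.80 only at f = 0.312.
- Repeated-measures ANOVA, between-groups factor, λ = f²Nm/(1 + (m − 1)ρ), with m = 4 measurements and assumed ρ = 0.5: λ = 0.0625 × 116 × 4/2.5 = 11.6, power 0.812. N = 112 gives 0.796, so 116 is the smallest equal-group N.

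The 116 can thus be reproduced, under assumed inputs, as an overall four-group test averaged over four measurements, baseline included. It is not shown to be wrong, but that test is not a PLDD-ESI comparison.

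**2. Chance of at least one false PLDD-ESI difference, two-arm reading.** Assume no treatment difference on any outcome at any visit, one two-sided test at 0.05 per score per visit, and each instrument counted as one score. There are six patient-reported scores: VAS, SF-36, ODI, Pain Detect, HADS and PSQI. With k independent tests the chance is 1 − 0.95^k; for k = 18, 1 − 0.95^18 = 0.603. For correlated tests, the probability that no test is significant was obtained by numerical integration over equicorrelated normal statistics. The documents give no correlations, so a range is shown.

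| Tests | ρ = 0 | 0.3 | 0.5 | 0.7 | 0.8 |
|---|---|---|---|---|---|
| VAS only, 3 visits (3) | 0.143 | 0.136 | 0.125 | 0.109 | 0.098 |
| Six scores, one visit (6) | 0.265 | 0.241 | 0.207 | 0.164 | 0.139 |
| Six scores, 1 and 6 months (12) | 0.460 | 0.397 | 0.319 | 0.232 | 0.186 |
| Six scores, 3 visits (18) | 0.603 | 0.509 | 0.398 | 0.277 | 0.216 |

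The 12-test row applies if the three-visit sentence covers every outcome. Clinical tests, laboratory values and MR are left out and would add to these figures.

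**3. Four-group reading.** Simulation, 29 per group, 20,000 trials: one-way ANOVA at 0.05, and only if it is significant, PLDD versus ESI within each contact group by a t test at 0.05. The plan names no post hoc test after ANOVA, so the t test is an assumption. The contact groups are assumed not to differ.

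| Outcome-visits | ρ = 0 | 0.3 | 0.5 | 0.7 | 0.8 |
|---|---|---|---|---|---|
| 6 | 0.197 | 0.180 | 0.158 | 0.127 | 0.111 |
| 18 | 0.477 | 0.407 | 0.324 | 0.225 | 0.179 |

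If the contact groups do differ, the ANOVA can be significant for that reason alone. With the gate fully open, two within-contact tests at one outcome-visit give 1 − 0.95² = 0.0975.

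**4. What 116 subjects offer for one named test.** Two-sided 0.05, no dropout, no gain from baseline adjustment.

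- Pooled, 58 v 58: power 0.80 at a standardised difference d = 0.525, 0.761 at d = 0.5, 0.570 at d = 0.4.
- Within one contact group, 29 v 29: power 0.80 at d = 0.749, 0.465 at d = 0.5.
- Pooled, adjusted for baseline with an assumed baseline-outcome correlation of 0.5: power 0.80 at d = 0.454, 0.869 at d = 0.5, 0.694 at d = 0.4.

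**The case against.** The best reply is that the intended primary is plain. VAS is the only pain-intensity measure, it is an entry criterion, and it is listed first. Moreover, the four-group ANOVA and the repeated-measures tests limit the number of looks, the 116 fits a coherent repeated-measures calculation, and 60% is a worst case that needs 18 independent tests and a rule, nowhere written, that any one significant result counts as efficacy.

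Part of this stands. Each individual test is valid at 0.05; only the family is uncontrolled. Scores repeated in the same patients are correlated, so the lower figures are the more realistic ones. Separate tests at each visit are an assumption, and the number of follow-ups is itself unclear. The 0.05 and 0.80 do belong to a four-group comparison; what is missing is its outcome, visit and treatment contrast.

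The rest does not remove the problem. VAS is never designated, and VAS alone at three visits already gives 10% to 14%. The repeated-measures and Friedman tests are described as comparing time points, with no treatment term. Conover is attached to Kruskal-Wallis only, with no stated adjustment, and an overall test at one outcome-visit does nothing across outcomes or visits. The absence of a success rule is part of the defect, not an answer to it.

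**Conclusion.** The concern holds. The documents name no primary outcome, visit, PLDD-ESI contrast, success criterion or multiplicity rule, so the error rate for the title question is not controlled. That conclusion comes from reading the text and depends on no assumed number.

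Its size does depend on assumptions: no true difference anywhere, each test at 0.05, any single significant result taken as efficacy, and assumed test counts and correlations from 0 to 0.8. On those terms the false-positive chance runs from about 10% (VAS alone, highly correlated visits) to 60% (18 independent tests). The gated four-group reading gives 11% to 48%. The plan should be amended; the sample size need not change.

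**What to change.** Before any outcome data are analysed, name one primary outcome, visit, contrast and model. A workable example is VAS at 6 months, PLDD versus ESI over both contact groups, by a linear model adjusted for baseline VAS and disc-root contact, at two-sided 0.05. If the sponsor prefers a within-contact contrast, the plan should say so and accept the lower power shown above.

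Report all other outcomes, visits, subgroup and pairwise results as exploratory, with confidence intervals and no efficacy claim. If further claims are wanted, list a few key secondaries in advance and adjust them by Holm. State which outcomes the three-visit sentence covers. Restate the power of the 116 subjects for the chosen primary, with its assumed effect size and any allowance for dropout, without enrolling more.

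The cost is SAP text, one model the plan does not now contain, and one power calculation, with no extra patients or visits. There are two downsides: an isolated P < 0.05 elsewhere can no longer be presented as confirmatory, and the restated power may differ from 0.80. If outcome analysis has already begun, the date of the choice must be disclosed, since naming a primary afterwards cannot restore error control.
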